In addition to the incentive for completing assessments, we have budgeted up to \$50 for a clean (i.e., no evidence of tobacco and cannabis use) sample as a contingency management incentive at the final postpartum assessment (T4).

Participants will be paid using Vincent, the University's approved payment system. There will be no compensation for partial completion of T1, T2, or T3. At T4, participants will be paid separately for completing all questionnaires (\$75) and interviews (\$25).

5. Recruitment materials: (attach all material to be seen or heard by subjects, including advertisements and scripts)

	Document	Category	Date Modified	Document History
View	Recruitment Scripts(1)	Recruitment Materials	2/3/2026	History
View	Intervention Screening Survey(2)	Recruitment Materials	1/30/2026	History
View	Recruitment flyer(1)	Recruitment Materials	1/6/2026	History

Study Aims

1. * Describe the purpose, specific aims, or objectives and state the hypotheses to be tested:

Guided by the PICTURe community collaborative, we will conduct a single group, proof-of-concept feasibility trial of a new intervention designed to address prenatal depressive symptoms to encourage tobacco and cannabis cessation. We will examine the initial feasibility and acceptability of the intervention using standard measures in addition to measures suggested by the collaborative. We hypothesize that 1) the intervention will be feasible to participants and 2) the intervention will be acceptable to participants.

The primary outcomes of the trial are the feasibility and acceptability of the novel intervention and abstinence from tobacco and cannabis use. Feasibility and acceptability of the intervention will be assessed using attendance, completion of intervention-related procedures, and the Acceptability of Intervention Measure (AIM). Abstinence will be measured by proportion of the participants who self-report no use of either substance and by calculating the proportion of participants with negative urine screens for THC and COT. Secondary outcomes include changes in depressive symptoms, tobacco, and cannabis use from the baseline assessment in pregnancy to 3 months postpartum.

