B2. Black (Mukerhjee et al., 2016) and sexual minority (Marsland et al., 2021; Ross et al., 2007) people experience more prenatal depressive symptoms, and depressive symptoms are associated with cigarette use and response to smoking treatment. There are bidirectional associations between depression and smoking in non-pregnant people (Bakhshaie et al., 2015; Breslau et al., 1998; Leventhal & Zvolensky, 2015; Needham, 2007; Pedersen & van Soest, 2009; Weinberger et al., 2017; Wilkinson et al., 2016). In rodent models, nicotine appears to be more reinforcing for depression-prone animals (Smethells et al., 2021; Tizabi et al., 1999) and in humans, depressed individuals experience nicotine as more reinforcing than do not depressed individuals (Perkins et al., 2010; Whitton et al., 2021). Former cigarette users with clinically significant depressive symptoms are more likely to remain abstinent when they receive cognitive-behavioral mood management intervention compared to former smokers with low levels of depressive symptoms (Haas et al., 2004; Kapson & Haaga, 2010). In contrast, cognitive-behavioral mood-management has been less efficacious for smokers who are not at high risk for depression (Brown et al., 2001; Haas et al., 2004; Kapson & Haaga, 2010). Thus, depressive symptoms are important targets in tailoring smoking cessation treatment in general. Similarly, among pregnant people, those with depressive symptoms (De Wilde et al., 2013, Hoffman & Hatch, 2000) and clinical depression (Goodwin et al., 2017b, Oh et al., 2017) are more likely to smoke cigarettes than are those without depressive symptoms. Depressive symptomatology prior to pregnancy is a robust predictor of persistent smoking during pregnancy (Tong et al., 2016). Depressive symptoms are common at the end of pregnancy (Bennett et al., 2004) with between 18% (Josefsson et al., 2001; Marcus et al., 2003) and 31% (Da Costa et al., 2000) of pregnant people reporting clinically significant symptoms of depression. Importantly, individuals with depression and depressive symptoms are motivated to quit smoking, and tobacco cessation does not increase depressive symptoms (Morozova et al., 2015). In fact, successful tobacco cessation during pregnancy is associated with better mood (De Wilde et al., 2013). Thus, prenatal depressive symptoms are common and an ideal target for smoking cessation interventions.

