Relatedly, we examined the effectiveness of two postpartum smoking relapse preventions as a function of prenatal depressive symptoms ([name] et al., 2020). People with clinically significant depressive symptoms late in pregnancy did not maintain smoking abstinence in the postpartum if they received a standard intervention with behavioral techniques to manage cigarette cravings (SUPPORT). However, as seen in Figure 3, those who were depressed late in pregnancy were more successful maintaining abstinence if they received a smoking abstinence intervention that was tailored to psychosocial factors such as mood (STARTS). These results highlight the importance of depressive symptomatology in postpartum tobacco abstinence and the significance of addressing prenatal depressive symptoms for long-term impact on maternal and child health. Thus, we propose to

invite people who use tobacco and cannabis and experienced elevated depressive symptoms during pregnancy to partner with us in an intervention development project to reduce tobacco-related health inequities.

Study Design

1. Total number of subjects to be enrolled at this site (enter -1 for chart reviews, banking, registries):

25

2. Describe and explain the study design:

This study is an experimental, single-arm feasibility trial.

3. Describe the primary and secondary study endpoints:

The primary outcomes of the trial is the feasibility and acceptability of the novel intervention and abstinence from tobacco and cannabis use. Feasibility and acceptability of the intervention will be assessed using attendance, completion of intervention-related procedures, and the Acceptability of Intervention Measure (AIM). Abstinence will be measured by proportion of the participants who self-report no use of either substance and by calculating the proportion of participants with negative urine screens for THC and COT. Secondary outcomes include changes in depressive symptoms, tobacco, and cannabis use from the baseline assessment in pregnancy to 3 months postpartum.

4. Provide a description of the following study timelines:

Duration of an individual subject's active participation:

Depending on gestation age at enrollment, subjects will actively participate in the study for approximately 6 to 12 months.

Duration anticipated to enroll all subjects:

9/30/2026

Estimated date for the investigator to complete this study (complete primary analyses):

10/1/2027

5. List the inclusion criteria:

- (1) <26 weeks of gestation

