- (2) English speaking
- (3) confirmed pregnant
- (4) plan to remain pregnant
- (5) use of combustible tobacco at least once a week during pregnancy, or at least once a week in the 3 months before pregnancy if stopped
- (6) use of cannabis at any frequency during pregnancy or in the 3 months before pregnancy if stopped

English speaking is a requirement since study materials are in English and intervention sessions will be conducted in English.

6. List the exclusion criteria:

- (1) current opioid use or active treatment for Opioid Use Disorder
- (2) unable to provide informed consent in English
- (3) under 18 years old

7. Will children or any gender, racial or ethnic subgroups be explicitly excluded from participation?

☒ Yes ☐ No

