De-identified data from the project will be saved in a database prepared for the study. The database will be password protected. The MPIs will make deidentified data collected from research participants available to other researchers and community partners after the study is completed and the final report has been generated. Data will be provided in the form of Excel files containing only ID codes as subject identifiers. No identifying information, including names, telephone numbers, or addresses, will be made available. Researchers requesting use of data must submit their request in writing to the MPIs, including the purpose for which they are requesting use of the data. These requests will be reviewed by the Investigators and will require engaging in a Data Use Agreement (DUA), in cooperation with the University of Pittsburgh. Data will be of sufficient quality to allow other investigators to validate and replicate research findings, consistent with NOT-OD-21-013. Updates on data sharing activities will be provided in annual progress reports to the funding organization.

- 3. If any research data is collected, stored, or shared in a paper format, address what precautions will be used to maintain the confidentiality of the data:**

Paper documents are kept in locked filing cabinets in an office of the Western Psychiatric Hospital at the University of Pittsburgh. Access to subject data records will be given only to the PI and study staff supervised by Drs [name] and [name].

Specimens and Related Data

1. * Data and Specimens will be stored:

Limited time (i.e., only until the study is completed)

2. * Indicate the type of specimen, describe where stored, and for how long:

Participants will be asked to provide one urine sample during their final assessment.

The sample will be tested for cotinine and THC and then disposed of immediately after this testing.

3. * How the specimens will be accessed and who will have access to the specimens:

The urine sample will be collected by the participant and accessed only by the research staff testing the sample.

4. * List the data to be stored or associated with each specimen:

The results of the THC and cotinine dip tests, date and time of the test, participant ID number, and documentation of payment for negative results will be recorded in a secure study database.

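### The primary abstinence proportion pools people already abstinent at baseline with people still using, so it mixes cessation with maintained abstinence

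*Protocol*

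**What the plan says.** **Who may enrol.** In Study Design, item 5, the tobacco criterion is met by at least weekly combustible use in pregnancy, "or at least once a week in the 3 months before pregnancy if stopped". The cannabis criterion is "use of cannabis at any frequency during pregnancy or in the 3 months before pregnancy if stopped". Enrolment is open until just before 26 weeks. Use during pregnancy need not be current use, so someone who stopped both substances in the first weeks of pregnancy also qualifies.

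**What is measured.** Study Aims, item 1 and Study Design, item 3 make abstinence a primary outcome alongside feasibility and acceptability: "Abstinence will be measured by proportion of the participants who self-report no use of either substance". A second, biochemical version of the outcome is the share whose urine tests negative for both THC and cotinine. Neither definition is conditional on use at T1.

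**How it is analysed.** Study Design, item 8 stratifies abstinence by race and sexual orientation. Use history appears there only in the comparison of feasibility. The item closes with a power statement in quit rates, 25% against 10%. Tobacco and cannabis use are asked about at T1 to T4 (Research Activities, item 1). For urine, "Participants will be asked to provide one urine sample during their final assessment" (Specimens and Related Data, item 2).

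**What the trial is for.** Study Aims, item 1 describes an intervention "designed to address prenatal depressive symptoms to encourage tobacco and cannabis cessation".

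**The concern.** A participant who is abstinent from both substances at T1 and remains so is counted as abstinent at every later assessment without having changed. A participant who was using at T1 must stop to be counted. These are two different quantities, relapse prevention and cessation, and one proportion over both groups estimates neither.

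The design has no concurrent control group, so nothing else removes the contribution of those who had already stopped. The pooled result then depends partly on how many such people happen to enrol. That matters if the figure is read as preliminary efficacy for cessation, or is carried forward as a quit rate when the next trial is planned.

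**Working it through.** **The plan's own figure.** Study Design, item 8 claims 70% power for quit rates of 25% against 10%. This was not reproduced. At two-sided alpha 0.05 it needs 79 per arm; at one-sided 0.05 it needs 60. Read instead as a single-arm exact test of 10% against 25% with n = 25, requiring at least 6 abstinent gives alpha 0.033 and power 62%, and at least 5 gives alpha 0.098 and power 79%. Alpha and sidedness are not stated, so these are trial values. The power figure and the two-arm wording are separate problems, and the present point does not depend on them.

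**Inputs for the pooling.**
- s, the share already abstinent from both substances at T1: not in the protocol; assumed 10–50%.
- m, the probability that such a person is still abstinent at follow-up: assumed 40–60%. Background section B1 says at least 40% of those who quit smoking in pregnancy resume postpartum, so at most about 60% maintain. That is for tobacco alone. Staying off both substances cannot be more frequent, hence the lower case of 40%.
- q, the quit rate among those using at T1: 10%, the control-arm rate in item 8, borrowed to represent little effect on users.

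**Formula.** Pooled abstinence P = s·m + (1 − s)·q. Therefore P − q = s·(m − q), which is positive whenever someone has already stopped and m exceeds q.

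**Results with q = 10%.**

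| s | m = 40% | m = 60% |
|---|---|---|
| 10% | 0.04 + 0.09 = 13% | 0.06 + 0.09 = 15% |
| 30% | 0.12 + 0.07 = 19% | 0.18 + 0.07 = 25% |
| 50% | 0.20 + 0.05 = 25% | 0.30 + 0.05 = 35% |

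The range is 13–35%, an excess over q of 3 to 25 percentage points. With s = 30% and m = 60%, 18 of the 25 points come from people who were already abstinent.

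**As a count out of 25.** The protocol sets no abstinence threshold, so take at least 6 of 25 (24%) purely as a yardstick. With q = 10% and m = 60%, the chance of reaching it is 3% if nobody had already stopped, 37% if 5 had, and 85% if 10 had (exact sum of two binomials).

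**Do the planned analyses of change remove this?** Cochran Q over k time points has a numerator that depends only on differences between column totals, and a denominator of k·ΣR − ΣR², where R is a participant's number of abstinent visits. A participant abstinent at every visit adds 1 to each column total, which leaves the numerator unchanged, and adds k·k − k² = 0 to the denominator. Such participants therefore do not inflate Q. But Q sees only the totals: if four users quit and four already-abstinent participants relapse over the same interval, the totals stay level and neither movement shows. The urine outcome has no T1 counterpart at all.

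**The case against.** The endpoint is called abstinence, a word that properly covers staying abstinent. Maintenance is also an intended target: session 2 includes relapse prevention, and the background is built largely on postpartum relapse. With at least 40% expected to resume smoking, remaining abstinent at T4 is a real outcome. This stands. Admitting people who have stopped is consistent with the programme, and the pooled proportion is not wrong as a description of abstinence. The difficulty arises when it is read as cessation.

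A reader might infer that the protocol itself labels the outcome a quit rate. It does not: item 8 speaks of self-reported abstinence, and quit rates appear only in the closing power sentence, which compares two arms.

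Change in use from baseline is a secondary outcome, and Cochran Q is not inflated by constant responders. That is genuine mitigation, though neither analysis as described separates the two groups.

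Reporting by subgroup is ordinary content for a statistical analysis plan, which is not shown. But this protocol names the strata for abstinence itself and leaves out use at T1.

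A reader might extend the point to depressive symptoms, since there is no symptom criterion at entry and section B2 says "cognitive-behavioral mood-management has been less efficacious for smokers who are not at high risk for depression". That extension is not made here. An entry criterion on symptoms is a design choice, and reporting change only in those with high T1 scores, without a control group, would invite regression to the mean.

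**Conclusion.** The point holds in a limited form. The eligibility criteria and the pooled primary proportion together mix cessation with maintained abstinence, and the result exceeds the quit rate among baseline users whenever maintenance is the more frequent of the two. The direction follows from the formula; the size does not follow from the protocol. The 13–35% range rests on an assumed share already stopped, on maintenance of 40–60%, and on a borrowed 10% quit rate.

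Two stronger readings are tempting. One takes 80% maintenance with half already stopped, giving 0.40 + 0.05 = 45%; the protocol's relapse figure does not support 80%. The other notes that s = 30% and m = 60% give exactly 25%, and concludes that the trial would meet its target with no effect on users. But 25% is one side of a two-arm comparison that a single-arm trial cannot make, no success threshold is set for abstinence, and that pair of values is only one among many.

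The change is worth making because it alters what the trial can conclude. It does not call eligibility or the feasibility aims into question.

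**What to change.** Classify each participant's use of tobacco and of cannabis at T1 from the questionnaires already scheduled, with the recall window stated. Report self-reported abstinence, and T4 urine-negative status, separately for:

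- participants using either substance at T1 (cessation);
- participants abstinent from both at T1 (maintained abstinence).

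Give the same split for each substance on its own. Present the results descriptively with exact confidence intervals, beside the pooled figure, and state that the pooled figure is not a quit rate. T1 status will rest on self-report, because no urine is taken then; a T1 urine test would be needed if the biochemical result is to be read as cessation.

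Eligibility need not change, and the reporting split needs no new data. The cost is precision. With 30% already stopped, the strata are about 7 and 18 people: 4 of 7 has an exact 95% interval of 18–90%, and 2 of 18 one of 1–35%. Formal testing within strata is not worthwhile.

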*** Identify the subgroups and provide a justification:**

We exclude individuals under age 18 from this work because the perinatal concerns and treatments for depression of individuals younger than age 18 are likely to differ from those of individuals 18 years of age or older and would require developmentally appropriate assessments and interventions.

8. Describe the power analysis used and cite your method of statistical analysis. If a power analysis is not possible, thoroughly justify the sample size required for the study, including appropriate literature citation (alternatively provide page reference in attached protocol):

Chi-square tests will be used to calculate differences in feasibility as a function of key intersecting identities (e.g., age, race, ethnicity, SM status) and use history variables. If feasibility is found to be significantly different by race or SM status, the analyses will be weighted to account for differences in attrition. We will assess the preliminary efficacy of the novel intervention to promote self-reported abstinence from tobacco and cannabis at the end of pregnancy (Time 3) and 12-16 weeks postpartum (Time 4). The proportion of self-reported abstinence among participants in the INT and EUC groups at Times 3 and 4 will be compared using chi-square tests of difference. We will stratify by race and sexual orientation to test for intersectional effects. Secondary analysis will examine differences in biochemically verified abstinence (urine dip test for presence of cotinine or THC) and depressive symptoms between INT and EUC using chi square tests and compare depressive symptoms (EPDS) scores in the two groups using two-sample t-tests. The Cochran Q test will be applied to self-reported tobacco and cannabis use across the 4 time points within the INT group to test whether there has been a change in the ratings over time. Next, a generalized linear mixed effects model (GLMM) with a logit link will be used to test the treatment effect (INT vs. EUC) and treatment by time interaction to test whether the rate of abstinence over time was steeper among the INT group compared to the EUC group. We have 70% power to detect a 15% difference in quit rates between INT and EUC, assuming a 25% intervention arm quit rate and 10% control arm quit rate.

Pregnant Women

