The intervention will be considered feasible and acceptable if participants attend more than 70% (i.e., >4) of sessions. Differences in feasibility also will be compared according to demographic variables and use history variables. Acceptability will be assessed by completion of self-monitoring forms, attendance during pregnancy, and the Acceptability of Intervention (AIM) measure. Retention also will be documented and will be defined as the proportion who provide data at 12-16 weeks postpartum relative to the total number enrolled. We will present these measures of feasibility and acceptability to the collaborative to solicit their input and may add other measures of feasibility and acceptability based on their recommendations.

2. * Describe the relevant prior experience and gaps in current knowledge including preliminary data. Provide for the scientific or scholarly background for, rationale for, and significance of the research based on existing literature and how it will add to existing knowledge:

B. SIGNIFICANCE

B1. People from marginalized communities are more likely to use tobacco during pregnancy (Agrawal et al., 2019) and are under-represented in tobacco treatment research (Weinberger et al., 2022). Rates of prenatal tobacco use have not decreased among Black people (Agrawal et al., 2019; Li et al., 2018) and are higher for sexual minority people (Beck et al., 2021; Gonzalez et al., 2019). At least 40% of individuals who quit smoking during pregnancy will resume smoking in the postpartum (Fingerhut et al., 1990; Rockhill et al., 2016), most of them within 100 days of delivery ([name] et al., 2022). Younger, less educated, Black people are more likely to relapse to smoking postpartum (Orton et al., 2018; Rockhill et al., 2016) and, on average, Black people smoke for more years prior to quitting (Jones

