A trained research team member will contact potential participants by telephone and/or email. We will use the relevant telephone and email scripts to describe the study and gauge interest. A screening survey will be used to determine eligibility. The screening survey will be programmed on REDCap and made available through Pitt+Me, the recruitment flyer, lab websites, and as a link sent to individuals who contact research staff directly. Once screened eligible, interested individuals will be contacted by the research assistant who will review and obtain consent for participation. After obtaining consent, the research team member will schedule the participant for their first prenatal session. The participant will then be texted or emailed a link to their baseline assessment questionnaires on REDCap.

Baseline Assessment (T1):

Participants will complete the following questionnaires as part of the baseline assessment: Demographics, EPDS, Smoking and Alcohol Use Questionnaire, Cannabis Use Questionnaire, Perceived Stress Scale-4, Major Experiences of Discrimination. Participants will be paid \$30 using the Pitt Vincent payment system when questionnaires are completed. The baseline assessment is estimated to take 30-60 minutes.

Prenatal Sessions

Participants will meet virtually with a study interventionist over the course of 6 prenatal sessions. Sessions will include education and discussions on the topics and strategies listed below. The scheduling timeline of prenatal sessions will depend on the gestational age of the pregnancy at time of enrollment and so will be determined on a case-by-case basis. Sessions will last up to 30 minutes.

1: Self-monitoring targets/ problem identification. This may include recognition of depressive symptoms, urges for tobacco and cannabis, how one might be used to manage withdrawal from the other.

2: Psychoeducation. This may include the teaching of rationale for addressing psychological distress/mood, relationship of trauma to mood and behaviors, model of cessation and relapse prevention/ learn how cannabis may hinder tobacco cessation and increase depressive symptoms.

3: Behavioral Activation. This may include identifying reinforcing activities and activities incompatible with tobacco and cannabis use.

4: Cognitive restructuring. This may include understanding/addressing dysfunctional thoughts about mood/stress and dysfunctional thoughts about tobacco and cannabis use.

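### Chi-square tests of feasibility force age and graded use history into groups, which roughly halves the power of those comparisons at n = 25

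*Protocol*

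**What the plan says.** Study Design item 8 fixes the test: "Chi-square tests will be used to calculate differences in feasibility as a function of key intersecting identities (e.g., age, race, ethnicity, SM status". The same sentence extends the test to use history. Study Aims item 1 announces the same comparisons: "Differences in feasibility also will be compared according to demographic variables and use history variables".

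The only attendance threshold is in Study Aims item 1: "The intervention will be considered feasible and acceptable if participants attend more than 70% (i.e., >4) of sessions". Research Activities item 1 gives the range of the count: "Participants will meet virtually with a study interventionist over the course of 6 prenatal sessions". The entry under "Total number of subjects to be enrolled at this site" (Study Design item 1) is 25, and item 2 adds: "This study is an experimental, single-arm feasibility trial".

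Item 8 attaches one consequence to the result: "If feasibility is found to be significantly different by race or SM status, the analyses will be weighted to account for differences in attrition". The document plans no analysis of attendance as a count, nor of age as a continuous variable.

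**The concern.** Attendance takes seven ordered values and age is continuous. A chi-square test of association uses neither the order nor the spacing. If attendance is cut at more than 4, a participant who attends no session counts the same as one who attends four. If age is split, everyone on one side of the split is treated alike. Each cut discards information, and with 25 participants there is little to spare.

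Whether attendance varies with participant characteristics is a stated question about a primary outcome, in a project concerned with disparities. The risk is that a real gradient with age or amount of use is reported as no difference in feasibility when the data already collected could have shown it more often.

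**Working it through.** **The plan's own power figure.** Item 8 says: "We have 70% power to detect a 15% difference in quit rates between INT and EUC", with 25% against 10%. That is a different comparison, and no power is given for the feasibility tests. It does not reproduce with 25 participants. Using n per arm = [1.96·√(2·0.175·0.825) + 0.524·√(0.25·0.75 + 0.10·0.90)]² / 0.15² = (1.053 + 0.276)² / 0.0225, the requirement is 79 per arm (two-sided). Splitting 25 as 12/13 gives 17% power. Nothing below depends on this figure.

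**Inputs from the protocol.** N = 25; attendance 0–6; more than 4 means 5 or 6 sessions; chi-square as the test; age named as a predictor.

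**Assumptions not in the protocol.** Two-sided 0.05; a median split of the predictor; 60% or 70% attending 5 or 6 sessions; the remainder spread over 0–4 in proportions 0.20/0.15/0.15/0.20/0.30; those attending 5 or 6 split 40/60.

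**Age or graded use history (both sides cut).** Draw predictor u and attendance tendency v = r·u + √(1 − r²)·e, with u and e standard normal, and cut v at normal quantiles to give 0–6 sessions. Form the 2×2 table (a, b, c, d) of median-split u by 5 or more sessions and compute N(ad − bc)² / [(a+b)(c+d)(a+c)(b+d)], rejecting above 3.84. Compare with Spearman's test on uncut u and the session count.

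| Latent r | Chi-square | Spearman, uncut |
|---|---|---|
| 0.3 | 13–14% | 25–27% |
| 0.4 | 21–23% | 43–44% |
| 0.5 | 32–33% | 62–63% |

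Type I error is about 5% for both. With 4,000 runs per setting the standard error is at most √(0.25/4000) = 0.8 points, so shifts of a point or two between runs are noise.

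**A different attendance distribution.** With 65% attending 5 or 6 sessions and half attending all six, power is 13% against 25%, 21% against 40%, 33% against 60%, 47% against 79% and 64% against 93% for r = 0.3 to 0.7. Adding a 45% scenario, chi-square keeps 52–71% of the uncut power overall. As a theoretical cross-check, two median splits under normality keep (2/π)² = 0.41 of large-sample efficiency, and one split keeps 2/π = 0.64.

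**Cutting only one side.** In the 65% scenario, keeping pass/fail but leaving age uncut (Mann-Whitney on age) gives 18%, 30% and 46% at r = 0.3, 0.4 and 0.5. That lies between the two columns, so about half of the loss comes from grouping age alone.

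**Race, ethnicity and sexual minority status (only attendance cut).** At 70% attending more than 4 and a 1.2 SD difference, Mann-Whitney on the count against chi-square on pass/fail gives about 74% against 61% for groups of 12 and 13 (13 points), and 57% against 53% for groups of 5 and 20 (4 points). A beta-binomial model of sessions gives, for example, 51% against 40% and 77% against 66% for 12/13, and 40% against 39% and 80% against 73% for 19/6.

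**Cell counts.** If 70% attend more than 4, expected failures are 12 × 0.3 = 3.6 and 13 × 0.3 = 3.9 in a 12/13 split, both below 5. Fisher's exact test, the usual substitute, gives 24% power at r = 0.5 where chi-square gives 32%.

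**The case against.** Four points on the other side have force.

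First, a reader might infer that half the power is lost for every comparison named. The figures do not support that. Race, ethnicity and sexual minority status are categorical to begin with, and the weighting rule is triggered only by race or sexual minority status, where the loss is modest.

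Second, a reader might take it as settled that the plan analyses attendance as pass/fail at more than 4. Item 8 names no cut and no feasibility variable. The sentence in Study Aims can be read as a criterion for the trial as a whole, and feasibility and acceptability are also assessed by completion of procedures and the acceptability measure. What stands is that a comparison between participants needs a participant-level outcome, that chi-square makes it categorical, and that no other threshold is offered. Using all seven levels would ignore their order and spread 25 people over at least 14 cells.

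Third, some use history is categorical by nature. The inclusion criteria distinguish use during pregnancy from use that stopped before it, and the double-cut figures do not apply to such items. Exact cut-points could properly be left to an analysis plan, but the choice of chi-square is already made here.

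Fourth, the proportion of a subgroup that meets the protocol's criterion answers a legitimate question. It can be shown descriptively without being the basis of the test.

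**Conclusion.** The point holds for age and for use history recorded as a frequency or amount. There, the stated test has roughly half the power of an uncut rank analysis at latent correlations of 0.3 to 0.5, under the assumptions listed above. For the identity variables the loss is about 4–13 points at a 1.2 SD difference. That figure depends on where the cut falls and which group attends more, so it is not an upper bound.

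A reader might also infer that the change makes these comparisons adequately powered. It does not: uncut power is still only 25–27% at r = 0.3 and 43–44% at r = 0.4, because the sample is 25. Severity is minor. It is a better use of data already collected, not a threat to the feasibility decision itself.

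**What to change.** In Study Design item 8, replace the chi-square sentence with a comparison of the number of sessions attended (0–6):

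- Age and use history recorded as frequency or amount, kept uncut: Spearman correlation, or ordinal or binomial regression of sessions out of 6 (allowing for overdispersion in the binomial case).
- Race, ethnicity, sexual minority status and categorical use history: Wilcoxon-Mann-Whitney, or Kruskal-Wallis for more than two groups.
- Report each with an estimate and confidence interval.
- Keep the proportion attending more than 4 sessions for the feasibility criterion, and show it descriptively by subgroup.
- State that these comparisons are exploratory and low-powered for modest associations at n = 25.

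The cost is wording only. Attendance, age and use history are already collected, and no participant or procedure is added. The same item also needs revision because its two-group comparisons do not fit a single-arm trial, so both changes can be made together.
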